- We will enroll and follow eligible children between ≥ 4 through < 8 years of age prospectively for one year. Using high-throughput multiplex PCR-based viral diagnostics, the identities of antecedent viral infections will be determined for each symptomatic URI, and during four surveillance periods. We hypothesize that rhinovirus will be the most common viral URI to predispose to acute bacterial sinusitis. This information can potentially direct the development of antiviral medication or viral vaccines.
- Using stringent clinical definitions for acute bacterial sinusitis, we will determine the incidence of sinusitis as a complication of viral URI. This has not been previously determined

and we hypothesize that sinusitis will complicate viral URI in 8% of cases in these young children.

Aim 2: To define relationships between the nasopharyngeal microbiome, viral illnesses, and progression to clinical sinusitis.

Nasopharyngeal samples and a pilot number of stool samples obtained before, during and after viral respiratory infections will be analyzed for bacterial species using array-based diagnostics (PhyloChip) and conventional semi-quantitative microbiologic techniques in two groups of children:

- a) those with viral URIs that resolve spontaneously and
- b) those whose URI progresses to acute bacterial sinusitis.

We hypothesize that the presence and density of sinopathogens and inhibitory commensal microbiota, together with modifications caused by infection with common respiratory viruses, will influence the likelihood of progression to acute bacterial sinusitis. Knowledge of these predictive elements will direct preventive strategies and treatment decisions.

The primary objectives of the study are as follows:

1. To determine a) the incidence of acute bacterial sinusitis in children ≥ 4 through < 8 years of age as a complication of an antecedent viral URI, b) if certain viruses are more likely than others to precipitate an episode of bacterial sinusitis and c) what percentage of sinus infections are, in fact, preceded by viral infection.

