
i) Data Analysis

Aim 1 - To assess the effects of virus type on progression to acute bacterial sinusitis, the type and number of background asymptomatic viruses, the season, and the interaction of season and background asymptomatic viruses and demographic variables, we will fit a generalized linear model to the URI episode data (1500 observations on 300 children, 0 = non progressing, 1 = progressing) using child as the main sampling unit and assuming a binomial distribution for the data. It is anticipated that the average number of URI episodes per child will be 5 per year. This model accounts for the potential correlation among the multiple episodes in each child. For predictors which take values of yes or no (such as virus type), we will have 80% power to detect the

difference between the percent of a particular virus type equal to 30% for the acute bacterial sinusitis group and 45% for the control group. We will test that rhinovirus is the most common viral URI to predispose to acute bacterial sinusitis using a Chi-squared test for goodness of fit. If rhinovirus accounts for 40% of the URIs leading to sinusitis and the second most common leads to 20% or less then we will have 80% power to conclude that rhinovirus is the most common viral antecedent to acute bacterial sinusitis.

The specimens obtained at baseline and during four other surveillance periods (approximately 1500 - 1800 specimens) will allow us to determine the changes due to season in background level of asymptomatic viral infection and the diversity of viruses. We will use robust multinomial regression using the R package multinomRob that accounts for over-dispersion due to the clustering of the URI episodes within children. This method of modeling multinomial data will allow us to assess the effect of season and the demographic variables on asymptomatic background viruses.

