To estimate the incidence of acute bacterial sinusitis as a complication of URI we will use a random effects generalized linear model assuming binomial distribution. We expect a total of 1500-1800 episodes of URI among the children and hypothesize that ABS will complicate 8% of these cases resulting in approximately 120 cases of acute bacterial sinusitis. If the true percent of viral URIs progressing to acute bacterial sinusitis is 8% then 1500 cases will give us 80% power to estimate the incidence with a 95% confidence interval no longer than 2.9%. If we were to observe exactly the 8% incidence the 95% confidence interval would be (6.68%, 9.49%).

Aim 2 - The episodes of acute bacterial sinusitis and uncomplicated URI chosen for PhyloChip analysis will be from two groups. The “acute bacterial sinusitis group” will consist of the first episode of acute bacterial sinusitis occurring among 50 randomly selected children who have one or more episodes of acute bacterial sinusitis. Only the first episode will be eligible to avoid data clustered within child. To avoid running all the PhyloChip analysis at the end of the study we will select the children in groups of 10 evenly spaced over the 52-months of enrollment and follow-up. An additional 50 matched control cases of uncomplicated URI will be selected (10 at a time) from the group of children who have not yet had an episode of acute bacterial sinusitis. The controls will be chosen so that their uncomplicated URI closely matches the case of acute bacterial sinusitis in calendar time. If a control child later develops acute bacterial sinusitis, the control child will become eligible to be chosen for the acute bacterial sinusitis group. If this occurs a different matched control will be chosen as a replacement. This process will result in a few extra PhyloChips being run but is necessary as the processing of PhyloChips is time consuming and cannot be delayed until the end of the study. In addition, the surveillance sample most closely preceding the episode of acute bacterial sinusitis and uncomplicated URI will also be analyzed using the PhyloChip.

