Innovation **This study will address numerous gaps in our knowledge of secondary bacterial infections (acute bacterial sinusitis, and also acute otitis media and bacterial pneumonia) of viral URI.** First, due to limitations in previously available viral diagnostics and a lack of stringent clinical criteria for acute bacterial sinusitis, there have been no previous studies to determine the incidence of acute bacterial sinusitis as a complication of viral URI. We propose to collect specimens quarterly during periods of health, and then multiple times during the course of an illness in order to gather a unique data set to define the relationship between viral URI and bacterial sinusitis. The high-throughput multiplex PCR-based viral diagnostics are ideal for identification of respiratory viruses in the over 5000 specimens to be collected. Second, no studies have been conducted to identify specific viral antecedents of acute bacterial sinusitis in children. Third, despite the immense clinical importance of respiratory infections in children, the nasopharyngeal microbiome of the child, whether in health, after exposure to common respiratory viruses, or during acute sinusitis, is virtually unknown. **Using culture-independent approaches will allow us to better understand the ecology of the microbiota of the nasopharynx and how these relationships are altered during viral infection or bacterial sinusitis.** In fact, to date there have been no previous studies of the nasopharyngeal microbiome in children.

In addition to the major knowledge gaps that we have identified in the preceding paragraph, this unique data set will allow us to address other outstanding questions of clinical importance including:

- a) Are children who experience closely spaced viral URIs more likely than those who experience infrequent URIs to develop acute bacterial sinusitis?
- b) What proportion of children with a first episode of acute bacterial sinusitis experience multiple episodes of sinusitis in one year?
- c) What proportion of episodes of acute bacterial sinusitis actually represent sequential episodes of very closely spaced viral URIs? (virus identified during episode of sinusitis is different from virus identified during the beginning of the respiratory illness)
- d) What proportion of episodes of acute “severe onset” bacterial sinusitis is caused by viral infections?

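### The model named for the primary incidence does not directly yield the share of URIs that progress, and the interval that illustrates it ignores clustering by child

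*Protocol*

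**What the plan says.** Aim 1 and primary objective 1a ask how often sinusitis complicates a viral URI. Aim 1 puts a value on it: "we hypothesize that sinusitis will complicate viral URI in 8% of cases in these young children". The incidence paragraph of Data Analysis repeats this as a share of episodes: "hypothesize that ABS will complicate 8% of these cases resulting in approximately 120 cases of acute bacterial sinusitis", out of 1500 to 1800 expected episodes.

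For estimation, the same paragraph says "we will use a random effects generalized linear model assuming binomial distribution". It does not give the link function or the distribution of the random effect. It also does not say whether the incidence is read from the intercept or averaged over children.

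The paragraph then gives two precision statements for 1500 episodes: 80% power for a 95% interval no longer than 2.9 percentage points, and an interval of 6.68% to 9.49% if exactly 8% is observed.

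The paragraph on virus type, earlier under Aim 1, describes the data as "1500 observations on 300 children, 0 = non progressing, 1 = progressing" and expects that "the average number of URI episodes per child will be 5 per year". It acknowledges possible correlation among a child's episodes but gives no size for it.

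**The concern.** Three parts of one paragraph describe different things. The target is a population-averaged proportion: progressing URIs over all URIs. The named model is conditional on the child. The interval belongs to a crude proportion that takes no account of the child.

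With no covariates, what a random-effects logistic model prints is an intercept. Back-transformed, that is the risk for a child whose random effect is zero, which under a normal random effect is the median child. When risks are well under 50% and differ between children, a minority of high-risk children pulls the average above the median, so the median-child risk is lower than the share of URIs that progress.

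Incidence is the first primary objective, and Aim 1 says it has not been determined before. An analyst who follows the paragraph literally and reports the intercept would publish a figure that is not the quantity defined in Aim 1. That figure could not be set directly against the 8% hypothesis or the printed interval.

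**Working it through.** **Inputs from the Protocol.** Hypothesised share 8%; 1500 episodes; 300 children; 5 episodes per child; about 120 cases (0.08 × 1500 = 120).

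**Input not in the Protocol (assumed).** Logit link, normal random intercept, between-child SD σ on the logit scale, varied over a range.

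**Step 1: reproduce the plan's figures.** For 120/1500:

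| Method | 95% interval |
|---|---|
| Exact (Clopper-Pearson) | 6.68% to 9.49% (length 2.81 points) |
| Wald | 6.63% to 9.37% |
| Wilson | 6.73% to 9.48% |

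Only the exact interval matches. With n = 1500 and p = 0.08, the binomial probability that the exact interval is no longer than 2.9 points is 79.2%, which agrees with the stated 80%. Both figures are therefore those of a simple proportion of independent episodes. Neither comes from the named model.

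**Step 2: what the intercept estimates.** Let child i have risk expit(β + σzᵢ), with zᵢ standard normal. The share of URIs that progress is the average of expit(β + σz) over z. Fix that average at 8%, solve for β by Gauss-Hermite quadrature, and report expit(β), the median-child risk.

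**Step 3: what clustering does to the interval.** The within-child correlation on the probability scale is ICC = (E[p²] − 0.08²)/(0.08 × 0.92). With 5 episodes per child the design effect is 1 + 4 × ICC. The width is 2 × 1.96 × √(0.08 × 0.92/1500 × design effect), which is 2.75 points when the design effect is 1.

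| Assumed σ | Median-child risk | ICC | Design effect | Width of 95% interval for the share (points) |
|---|---|---|---|---|
| 0.25 | 7.81% | 0.005 | 1.02 | 2.77 |
| 0.5 | 7.27% | 0.019 | 1.08 | 2.85 |
| 0.75 | 6.48% | 0.045 | 1.18 | 2.98 |
| 1.0 | 5.56% | 0.080 | 1.32 | 3.15 |

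Up to σ = 0.5 the median-child risk stays inside the printed interval. At 0.75 it is just below the lower limit of 6.68%, and at 1.0 it is more than a point below.

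**Step 4: check by simulation.** 150 studies per setting, 300 children, Poisson mean of 5 episodes, maximum-likelihood fit, true share 8%:

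| σ | Back-transformed intercept (mean) | Same model, integrated over the random effect | Crude share |
|---|---|---|---|
| 0 | 7.75% | 7.98% | 7.98% |
| 0.5 | 7.23% | 8.00% | 8.00% |
| 1.0 | 5.61% | 7.93% | 7.92% |

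The fitted model recovers the target once it is averaged over children. Only the unaveraged intercept is off.

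**Step 5: dependence on the link.** The direction is not peculiar to the logit. With a log link the median risk is 0.08 × exp(−σ²/2), which is 4.85% at σ = 1.0 on the log scale. With a probit link it is Φ(Φ⁻¹(0.08) × √(1 + σ²)), which is 5.81% at σ = 0.5 on the probit scale. An identity link would show no gap.

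**The case against.** The strongest reply is that the Protocol never commits to reporting the intercept. It names a model and stops. The same model gives the population-averaged share by integration, and Aim 1, the 8% and the 120 cases all indicate that this share is wanted. On that reading the random effect is there only to allow for repeated episodes. Link and back-transformation are often settled in a statistical analysis plan, and none is shown here. This stands. A reader might infer that the reported incidence will be too low, but the text does not support that: it would take a non-linear link, real differences between children and an unaveraged intercept, and the Protocol states neither the link nor the reporting rule.

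The size is also open. An ICC of 0.08 at σ = 1.0 sounds modest, yet it implies that 95% of children have per-URI risks between about 0.8% and 29%. That is wide for otherwise healthy children from whom predisposing conditions have been excluded (Eligibility and enrollment). At σ of 0.5 or less the shift is under 0.75 points.

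A reader might also infer that the model would mis-weight children with many URIs, because Innovation, question a), asks: "Are children who experience closely spaced viral URIs more likely than those who experience infrequent URIs to develop acute bacterial sinusitis". That is an open question, not a stated belief, and no link between URI frequency and risk is given from which an effect could be sized.

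What the reply does not remove is the mismatch within the paragraph. The model is conditional, the target is marginal, and the printed interval comes from neither the named model nor any clustered analysis. That goes beyond a detail left for later.

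**Conclusion.** The point holds in conditional form. The incidence paragraph names a model whose direct output is not the share defined in Aim 1, and illustrates it with an exact interval for independent episodes. If the back-transformed intercept is reported, the incidence is understated by about 0.2 points at an assumed σ of 0.25, 0.7 at 0.5, 1.5 at 0.75 and 2.4 at 1.0, against a true 8%. The bias is small when children differ little and material when they differ a lot.

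These sizes rest on a logit link, a normal random intercept and an SD that the Protocol does not give. Some variation between children fits the Protocol's own thinking: it allows for within-child correlation, and Aim 2 supposes that nasopharyngeal bacteria influence progression. Neither fixes its size. The bias disappears if the model is averaged over children. Separately, the printed interval is too narrow to whatever extent episodes within a child are positively correlated.

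**What to change.** In the incidence paragraph, name the reported quantity as the population-averaged proportion: total progressing URIs over total URIs. Give it a 95% interval that allows for clustering by child, from an intercept-only GEE with working independence and robust standard errors, or from a bootstrap that resamples children.

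If the random-effects model is kept, state the link and the random-effect distribution, and state that the incidence and its interval are obtained by integrating over that distribution.

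Add one sentence saying that the interval of 6.68% to 9.49% and the 2.9-point length assume independent episodes and will widen with within-child correlation.

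The cost is a few sentences of analysis text, written before the incidence is analysed. No data collection or sample size change is needed.

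### The precision promised for the sinusitis incidence treats 1,500 URIs as independent, although the plan places them in 300 children and models the clustering

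*Protocol*

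**What the plan says.** The precision for the incidence is in Protocol section 4 (Study procedures), item i (Data Analysis), under Aim 1. It makes two claims. The first concerns assurance: "1500 cases will give us 80% power to estimate the incidence with a 95% confidence interval no longer than 2.9"%, on the premise that the true risk is 8%. The second concerns the interval itself: "If we were to observe exactly the 8% incidence the 95% confidence interval would be (6.68%, 9.49"%).

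The same text describes data that are not independent. The Aim 1 model for virus type uses "1500 observations on 300 children", with an expected average of five episodes per child per year, and is said to allow for possible correlation between a child's episodes. For the incidence itself, "we will use a random effects generalized linear model assuming binomial distribution". The expected yield is a range: "We expect a total of 1500-1800 episodes of URI among the children".

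Two neighbouring analyses show the same awareness. The multinomial model for background viruses is chosen because it "accounts for over-dispersion due to the clustering of the URI episodes within children". For the PhyloChip cases in Aim 2, "Only the first episode will be eligible to avoid data clustered within child".

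The protocol gives no ICC, random-effect variance or design effect, and it does not say that the precision figures assume independence.

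**The concern.** If some children are more prone than others to progress from URI to sinusitis, five episodes from one child carry less information about the incidence than five episodes from five children. An interval that allows for this is wider than the independent-episode interval. The protocol's own premise makes such differences plausible: it hypothesises that the nasopharyngeal microbiome strongly affects risk, and it lists child-level traits such as age, siblings, daycare and asthma as candidate predictors.

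Incidence is primary objective 1a, and this is the only precision stated for it. A reader would expect the reported interval to be about 2.8 points wide, with a four-in-five chance of at most 2.9. Neither expectation holds at 1,500 episodes if the outcomes are positively correlated within child.

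**Working it through.** **Inputs from the Protocol (section 4.i, Aim 1):** true incidence 8%; 1,500 to 1,800 episodes; 300 children; mean of 5 episodes per child; about 120 cases (0.08 × 1,500).

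**Assumed, because the document gives no value:** ICC of 0.02, 0.05 or 0.08 on the observed (0/1) scale, and Poisson-distributed episode counts per child.

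**Step 1: reproduce the stated figures.** The Clopper-Pearson 95% limits for x = 120, n = 1,500 are the 2.5% quantile of Beta(120, 1381) and the 97.5% quantile of Beta(121, 1380). These are 6.677% and 9.490%, a width of 2.81 points, and they match the protocol to both decimals. Wald (6.63-9.37), Wilson (6.73-9.48), Agresti-Coull (6.73-9.49), Jeffreys (6.71-9.45), logit (6.73-9.48) and continuity-corrected Wilson (6.70-9.52) do not match both limits.

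For the assurance, sum the Binomial(1500, 0.08) probabilities over all counts whose Clopper-Pearson width is at most 2.9 points. The result is 79.2%, which is the stated 80%. Both claims are therefore independent-episode results with a design effect of 1.

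**Step 2: design effect.** With mean cluster size m and coefficient of variation cv, DE = 1 + [(1 + cv²)m − 1] × ICC. Poisson counts with m = 5 have cv² = 1/5, so DE = 1 + (1.2 × 5 − 1) × ICC = 1 + 5 × ICC. This gives 1.10, 1.25 and 1.40.

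**Step 3: interval at an observed 8%,** using Clopper-Pearson on the effective number n/DE:

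| DE (ICC) | 1,500 episodes: n/DE | 95% interval | Width | 1,800 episodes: n/DE | 95% interval | Width |
|---|---|---|---|---|---|---|
| 1.00 (0) | 1,500 | 6.68-9.49% | 2.81 | 1,800 | 6.79-9.35% | 2.56 |
| 1.10 (0.02) | 1,364 | 6.62-9.57% | 2.95 | 1,636 | 6.73-9.42% | 2.69 |
| 1.25 (0.05) | 1,200 | 6.53-9.68% | 3.15 | 1,440 | 6.65-9.52% | 2.87 |
| 1.40 (0.08) | 1,071 | 6.45-9.79% | 3.34 | 1,286 | 6.58-9.62% | 3.04 |

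The width at 8% reaches 2.9 points at DE 1.06 for 1,500 episodes, an ICC of about (1.06 − 1)/5 = 0.012. For 1,800 episodes it does so at DE 1.27.

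**Step 4: assurance.** This was simulated with 20,000 runs per scenario. Child risks were logit-normal, calibrated to a marginal 8% and the stated ICC, with Poisson episode counts. The estimate is total cases over total episodes, with a child-level robust variance.

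| ICC | Mean width, 300 × 5 | Chance of width ≤ 2.9, 300 × 5 | Width met with 80% assurance, 300 × 5 | Chance of width ≤ 2.9, 300 × 6 | Chance of width ≤ 2.9, 360 × 5 |
|---|---|---|---|---|---|
| 0 | 2.74 | 84% | 2.88 | over 99% | over 99% |
| 0.02 | 2.87 | 57% | 3.03 | 93% | 96% |
| 0.05 | 3.06 | 24% | 3.25 | 61% | 72% |
| 0.08 | 3.24 | 10% | 3.47 | 29% | 42% |

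Column labels give children × mean episodes. A beta distribution for child risk gives nearly the same results for 300 × 5 (57%, 24% and 9% at ICC 0.02, 0.05 and 0.08). With exactly five episodes per child the loss is a little smaller (62% at ICC 0.02, 30% at 0.05).

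**The case against.** The strongest reply is that the protocol's sums are correct. Only a clause stating independence is missing, and every shortfall above comes from ICCs that the document does not give. This is right as to size: the document fixes the direction of the error but not its amount. At ICC 0.02 the effect is small, and the mean robust width of 2.87 is still under 2.9. The exclusion criteria remove some high-risk children and so some heterogeneity.

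Second, the methods differ. The protocol's assurance is for Clopper-Pearson (79%), whereas the simulated series uses a robust Wald interval that starts at 84% with no clustering. The series should be read against its own starting point. Because that start is the more favourable one, the switch does not create the shortfall.

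Third, the planned analysis is a random-effects model, and these figures are a marginal approximation to it. This also stands. An interval back-transformed from that model's intercept concerns the risk of a typical child (about 7.3%, 6.3% and 5.6% at ICC 0.02, 0.05 and 0.08), not the marginal 8%. In a small simulation of 200 runs per scenario its median width was about 2.98 points near ICC 0 and 3.7 at ICC 0.02-0.08. That does not support 2.9 points either, but replacement figures must say which quantity they describe.

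Fourth, the remarks on over-dispersion and on first episodes belong to other analyses. They show awareness of clustering and no more. The case needs only the 300-children structure and the random-effects plan for the incidence.

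Last, the practical consequence is limited: the analysis itself allows for clustering, and 1,800 episodes would offset a design effect of up to 1.27 for the interval at 8%. But the protocol ties both claims to 1,500.

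**Conclusion.** The point holds. Both precision figures are exact binomial results for 1,500 independent episodes and do not describe the clustered data and model that the protocol plans. For any positive within-child correlation they are too favourable at 1,500 episodes. If the ICC is zero, they stand as a marginal exact interval.

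The size depends on assumed ICCs. Over 0.02 to 0.08 the interval at 8% widens by about 0.1 to 0.5 points (2.95 − 2.81 = 0.14; 3.34 − 2.81 = 0.53). The claimed four-in-five assurance of 2.9 points becomes roughly one in two to one in ten. The interval changes modestly; the assurance changes a good deal, because 2.9 points leaves almost no margin.

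The planned model is not at fault, and no test, sample size or go/no-go decision rests on the figure. It should be corrected because it is the only precision given for the first primary objective.

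**What to change.** In section 4.i, Aim 1, restate the interval, width and assurance under a declared ICC or design-effect range, for both 1,500 and 1,800 episodes, using the clustered method intended for the analysis. Drop or recompute the 80%/2.9-point claim. State whether the reported incidence is the marginal proportion of episodes or the model's child-specific risk, so that the planning figure and the reported interval describe the same quantity.

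As an illustration, labelled as a marginal, cluster-robust approximation: at 1,500 episodes and a design effect of 1.25, the interval at an observed 8% is about 6.5-9.7%, and a width of about 3.25 points is met with 80% assurance.

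If the present figures are kept, add one clause saying that they assume no within-child correlation.

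The cost is wording and one recalculation. The design, sample size and planned model do not change.
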